Community-Based Participatory Research: If you are conducting [community-based participatory research \(CBPR\)](#), describe strategies for involvement of community members in the design and implementation of the study, and dissemination of results from the study.

Research Repositories: If the purpose of this submission is to establish a Research Repository (bank, registry) indicate whether the material you plan to collect would or would not be available from a commercial supplier, clinical lab, or established IRB approved research repository. Provide scientific justification for establishment of an additional repository collecting duplicate material. Describe the repository design and operating procedures. For relevant information to include, see the UK Research Biospecimen Bank Guidance [\[PDF\]](#) or the UK Research Registry Guidance [\[PDF\]](#)

This will be a pre-post study built to replicate the introduction of angiotensin II into the clinical practice at UK HealthCare as outlined in the study protocol. 10 patients will be recruited, who receive normal standard of care, and consented to obtain plasma renin levels and biomarkers of renal function (three blood draws). After 10 patients, the next 20 patients meeting eligibility criteria will receive angiotensin II, they will also have blood drawn (four blood draws) to evaluate renin and renal biomarker response to angiotensin II.

Attachments

[Back to Top](#)

Study Population: Describe the characteristics of the subject population, such as anticipated number, age range, gender, ethnic background and health status. Identify the criteria for inclusion and exclusion. Explain the rationale for the use of special classes such as fetuses, pregnant women, children, institutionalized, adults with impaired consent capacity, prisoners, economically or educationally disadvantaged persons or others who are likely to be vulnerable.

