Once subjects are identified per the above process, an assessment will be made as described in form T by the study team member of whether the patient can provide informed consent. If ineligible, a legally authorized representative will be approached regarding the study. Informed consent will be sought once the patient meets the eligibility criteria as defined in the study protocol. If the legally authorized representative is not physically in the hospital due to visiting restrictions due to COVID-19, an electronic consent process will be sought as follows. The patient's LAR will be contacted via telephone and approached about the study in the same way that the LAR would be if they were physically present. If the LAR is interested in pursuing further, a member of the study team will send the LAR a RedCap link (<https://redcap.uky.edu/redcap/surveys/?s=7LWKY4JETE>) that has been designed for e-consent in this study. A member of the study team will walk the LAR through the e-consent document, which mirrors the written informed consent document exactly, and answer any questions along the way. If the LAR consents, they will sign the document using the e-sign feature in RedCap. A member of the study team will email the LAR back with a copy of the signed e-consent form.

[Back to Top](#)

Research Procedures: Describe the research procedures that will be followed. Identify all procedures that will be carried out with each group of subjects. Differentiate between procedures that involve standard/routine clinical care and those that will be performed specifically for this research project.

Control group (n=10): Standard of care will be followed for all aspects of care. The only procedure specifically involving research will be blood collection once the patient meets inclusion criteria (time T), 24 hours later (time T + 24 hours), and when the patient no longer requires vasopressor agents to support their blood pressure (defined as off of vasopressors for at least 4 hours). If the patient ceases vasopressor agents within 12 hours of the second blood draw, the third and final blood draw will not be collected.

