Intervention group (n=20): Standard of care will be followed for the management of septic shock. At which point the patient meets the inclusion criteria of the study, the patient's treating physician will be approached about the opportunity to offer angiotensin II to the patient. If the treatment team wishes to pursue, the patient or their LAR will be approached for written informed consent. Angiotensin II will be dosed per the protocol, and the patient will receive blood draw at the time they meet inclusion criteria (time T), 3 hours later (T+3), and 24 hours from angiotensin II initiation (T+24 hours), and when the patient no longer requires vasopressor agents to support their blood pressure (defined as off of vasopressors for at least 4 hours). If the patient ceases vasopressor agents within 12 hours of the third blood draw, the fourth and final blood draw will not be collected. All other aspects of the patient's care will be per the standard of care in the medical intensive care unit. Blood samples will be centrifuged, plasma extracted, and stored at -80 C. Commercial ELISAs will be used for analysis of renin and renal biomarkers (cystatin C, NGAL, renin, angiotensin II, angiotensin 1-7). COVID specification. Testing positive is a known exclusion criteria for the study. If a patient has results when evaluated for the study, this will be straightforward. However, if the test is pending while the patient is eligible for study entry, this will not make the patient ineligible for the study. If, in the opinion of the attending physician, COVID-19 is highly likely the patient will not be approached for informed consent. Otherwise, if COVID-19 test is pending, the patient or LAR will be approached for informed consent. If the test results as negative, study procedures will be performed as planned. If the test returns positive, the patient will be informed and dropped from the study. We will use their baseline information collected up to that point, but they will no longer receive blood draws or study medication (angiotensin II) once confirmed COVID positive. A case series of angiotensin II has been published in COVID 19

patients, and given the acuity of the disease state in question, it would not be appropriate to wait for a negative COVID test in our judgement.

Attachments

Data Collection: List the data or attach a list of the data to be collected about or from each subject (e.g. interview script, survey tool, data collection form for existing data).

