If the research includes survey or interview procedures, the questionnaire, interview questions or assessment scales should be included in the application (use attachment button below).

The data collection instrument(s) can be submitted with your application in draft form with the understanding that the final copy will be submitted to the IRB for approval prior to use (submit final version to the IRB for review as a modification request if initial IRB approval was issued while the data collection instrument was in draft form).

Note: The IRB approval process does not include a statistical review. Investigators are strongly encouraged to develop data management and analysis plans in consult with a statistician.

Demographics (age, sex, race, past medical history), chief complaint, sequential organ failure assessment score, vasopressor dosing, lactate, requirement for mechanical ventilation, requirement for renal replacement therapy, serum creatinine values, blood pressure. Monitoring of side effects including: venous thromboembolism, arrhythmia, extremity hypoperfusion, delirium, new ischemic event, new infection), and any others deemed pertinent per the institution that may be related to angiotensin II. Patient outcomes including: in-hospital mortality, ICU and hospital length of stay, acute kidney injury and needed for renal replacement therapy. Lab values for renin and functional biomarkers of renal function at the time points described (cystatin C, NGAL, angiotensin II, angiotensin 1-7).

Attachments

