Following enrollment of the 10 patients in the control arm and 10 patients in the angiotensin II arm (i.e. half of the 20 patients that will ultimately receive the drug), we will evaluate the risk of venous thromboembolism and any additional reported thrombotic reports from the 10 patients that have received angiotensin II. Groups will be compared using a Fisher's exact test given the small sample size. Given the concern for safety, if the p-value is 0.15 or less with increased thrombotic events in the angiotensin II group, the open-label study will be stopped. For example, assuming a baseline rate of thrombotic events of 1/10 (10%) in the control arm, if 5/10 patients in the angiotensin II group (50%) experienced a thrombotic event, a Fisher exact test yields p=0.141 and the open-label use of angiotensin II would be stopped due to concern for safety. If thrombotic event differences do not meet this threshold, we will continue with the enrollment of an additional 10 patients to meet the 20 patient enrollment set.

[Back to Top](#)

Subject Complaints: Describe procedures (other than information provided in consent document) for handling subject complaints or requests for information about the research. The procedures should offer a safe, confidential, and reliable channel for current, prospective, or past research subjects (or their designated representative) permitting them to discuss problems, concerns and questions, or obtain information.

Subject complaints will be directed to the primary investigator, who will contact the subjects to discuss their concerns, including potential withdraw from the study or use of their information. If a subject has any concerns or questions about his/her rights as a volunteer in this research, they will be advised to contact staff in the Office of Research Integrity (ORI).

Does your research involve **Non-English Speaking Subjects or Subjects from a Foreign Culture?**

Yes No

—Non-English Speaking Subjects or Subjects from a Foreign Culture—

Describe how information about the study will be communicated to potential subjects appropriate for their culture, and if necessary, how new information about the research may be relayed to subjects during the study.

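### The thrombosis stopping look is tied to enrollment with no event window or minimum follow-up, so late treated patients may be counted as event-free

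*Combined protocol and SAP*

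**What the plan says.** Data and Safety Monitoring, repeated under Interim Analysis, sets one safety look: "Following enrollment of the 10 patients in the control arm and 10 patients in the angiotensin II arm". It covers venous thromboembolism and "any additional reported thrombotic reports from the 10 patients that have received angiotensin II". The arms are compared by Fisher's exact test. The study stops if p is 0.15 or less with more events on angiotensin II. Otherwise: "If thrombotic event differences do not meet this threshold, we will continue with the enrollment of an additional 10 patients". The worked example is 5/10 treated v 1/10 control, p=0.141, stop.

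Other sections that bear on the timing and counting of events:

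- Study Design enrolls the arms in sequence: "After 10 patients, the next 20 patients meeting eligibility criteria will receive angiotensin II".
- Data Collection has "Monitoring of side effects including: venous thromboembolism" at the head of its side-effect list, with no period attached.
- Research Procedures times the blood draws, not the thrombotic events. Time T is described for controls as "blood collection once the patient meets inclusion criteria (time T" and for treated patients as "the patient will receive blood draw at the time they meet inclusion criteria (time T". The treated arm's T+24 draw, however, is counted from the start of angiotensin II.
- Research Procedures also drops patients whose COVID-19 test returns positive: "We will use their baseline information collected up to that point".

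The attachment list under Additional Information includes a detailed protocol file that is not among the supplied documents.

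**The concern.** A count of thrombotic events means little unless the period over which it is taken is known. The rule says whom to count but not for how long. Every control is enrolled before any treated patient, so by the time ten treated patients are in, the controls have probably had ample follow-up. The most recent treated patients may have had almost none. Any shortfall in follow-up therefore falls mainly on the arm whose harm the rule is meant to detect.

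The decision at stake is whether 10 more patients receive the drug. With 10 per arm, one event can reverse it. The handling of a patient dropped for COVID-19 matters for the same reason: the text does not say whether a thrombosis after the drop counts.

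**Working it through.** **Inputs.** From Data and Safety Monitoring: 10 patients per arm, threshold p≤0.15 with more treated events, example rates 10% (control) and 50% (treated). From Background: labelled thrombotic rates of 13% v 5%. The number of late patients and the share of their events visible at the look are assumptions; the documents give neither.

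**1. Reproduce the plan's figure.** For 5/10 v 1/10 there are 6 events among 20 patients, with C(20,6)=38,760 arrangements.
- P(5 treated) = C(10,5)·C(10,1)/38,760 = 2,520/38,760 = 0.0650
- P(6 treated) = C(10,6)·C(10,0)/38,760 = 210/38,760 = 0.0054
- The upper tail is 0.0704. With equal arms the two-sided value is twice that, 0.1409, which matches the stated 0.141. The example is therefore two-sided.

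**2. One treated event not yet seen, patient kept in the denominator.** For 4/10 v 1/10, C(20,5)=15,504.
- Upper tail = (210·10 + 252·1)/15,504 = 2,352/15,504 = 0.1517
- Two-sided p = 0.3034: continue.

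**3. The same patient left out instead.** For 4/9 v 1/10, C(19,5)=11,628.
- Upper tail = (126·10 + 126·1)/11,628 = 1,386/11,628
- The only outcome in the other tail that is no more probable than the observed one is 0 treated events: C(10,5)/11,628 = 252/11,628
- Two-sided p = 1,638/11,628 = 0.1409: stop.

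**4. Chance of stopping at 50% v 10%.** Enumerating the 10 v 10 tables, the smallest treated count that stops is 4, 5, 7, 8 or 9 for 0, 1, 2, 3 or 4 control events. Then P(stop) = Σ P(c control events) · P(treated events ≥ boundary for c).

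| Control events | P(c), Binomial(10, 0.1) | Boundary | P(treated ≥ boundary), Binomial(10, 0.5) | Product |
|---|---|---|---|---|
| 0 | 0.3487 | 4 | 0.8281 | 0.2887 |
| 1 | 0.3874 | 5 | 0.6230 | 0.2414 |
| 2 | 0.1937 | 7 | 0.1719 | 0.0333 |
| 3 | 0.0574 | 8 | 0.0547 | 0.0031 |
| 4 | 0.0112 | 9 | 0.0107 | 0.0001 |

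The sum is 0.567; larger control counts add a negligible amount.

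**5. Immature treated follow-up.** Let the last k treated patients each show an event with probability 0.5·f, where f is the visible share. Controls are complete and the denominator stays at 10. The last column drops those k patients from the treated denominator and recomputes the test.

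| k | No events visible (f=0) | Half visible (f=0.5) | Late patients left out |
|---|---|---|---|
| 1 | 47% | 52% | 66% |
| 2 | 37% | 47% | 62% |
| 3 | 26% | 42% | 51% |

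The reference with complete follow-up is 57%.

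**6. At 13% v 5%.** The same sum gives 2.0% with complete follow-up, and 1.3% if the last treated patient shows no events but stays in the denominator.

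**The case against.** Several points on the other side have force.

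- *The text does not say the look happens at the 10th enrollment.* It says following enrollment, and a later look fits that wording. A reader might infer that treated events will be missed; the documents support only that they can be. Mature control follow-up is likewise an inference from the sequential design. This limits the claim. It does not supply the missing timing, because an immediate look and a much later one both comply with the rule.
- *The direction depends on the denominator.* If late patients are left out, the example still stops, and the chance of stopping is above 57% for one or two such patients. This stands, so a flat statement that the rule is biased toward continuing goes too far. Keeping 10 v 10 is nevertheless the plainer reading of the rule and of its example.
- *The zero-visibility illustration is severe.* This also stands. With half the events visible the loss is about 5 to 15 percentage points, against 9 to 30.
- *The next 10 patients are already conditional on the look.* True, but the condition does not say how much follow-up the look must rest on.
- *The window may be in the detailed protocol that was not supplied.* It may. The sections that state the rule should then cite it.

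A reader might also take sidedness as unresolved, or conclude that a one-sided test is required. The worked example settles the first: 0.141 is the two-sided value. Nothing in the documents requires the second.

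**Conclusion.** The point holds in a limited form and should be fixed. On the supplied text, the stopping rule has no event window and no minimum follow-up, and the enrollment order puts any immaturity mainly in the treated arm. If late patients stay in the denominator of 10 as event-free, one unseen event turns the protocol's own stop example (p=0.141) into a continue (p=0.303). At the example rates, the chance of stopping falls from 57% to between 26% and 52%, depending on whether one to three late patients show none or half of their events.

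Those percentages are illustrations. They assume complete control follow-up, a fixed denominator, and true rates of 50% and 10%.

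It would be tempting to read this as the reason the rule is weak. The figures do not support that: at the labelled 13% v 5%, it stops only 2.0% of the time with complete follow-up. Ten patients per arm is the main limit, and better timing will not remove it. Confidence is medium, because the detailed protocol was not available.

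**What to change.** In Data and Safety Monitoring and in Interim Analysis:

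1. Define one thrombotic-event window of equal length in both arms, with the length chosen by the team.
2. Start it from one time point defined the same way in both arms. The two uses of T in the intervention-group procedures (meeting the inclusion criteria, and starting angiotensin II) must be reconciled first.
3. Do the look only after the 10th treated patient has completed the window or died, and hold the next 10 until then.
4. Count every patient who received any angiotensin II among the treated. State whether events after a COVID-positive drop count, with the same rule in both arms.

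If the detailed protocol already gives a window, cite it in both sections and check it against these four items. No change of test, threshold or sidedness is needed for this point.

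The cost is a few sentences and an enrollment pause of up to one window after the 10th treated patient.

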[To view what materials are currently attached to your application, go to "Application Links" in the menu bar on the left and click "All Attachments".]

Attachments

Attach Type	File Name
AddInfoConsiderations	57411 [name].pdf

Statistical Analysis

Continuous data will be described using medians and interquartile ranges. Discrete data will be described as counts and percentages. Changes in biomarker measurements will be calculated by subtracting the biomarker measurement at subsequent timepoint from the baseline biomarker measurement at enrollment. Assuming non-normal distributions of biomarker measurements with extreme elevations as well as skewness of the data for lengths of stay, continuous variables will be compared using the Mann-Whitney U test while discrete data will be compared between groups using chi-squared or Fisher's exact test as appropriate. A p-value <0.05 will be considered statistically significant.

Interim Analysis

Following enrollment of the 10 patients in the control arm and 10 patients in the angiotensin II arm (i.e. half of the 20 patients that will ultimately receive the drug), we will evaluate the risk of venous thromboembolism and any additional reported thrombotic reports from the 10 patients that have received angiotensin II. Groups will be compared using a Fisher's exact test given the small sample size. Given the concern for safety, if the p-value is 0.15 or less with increased thrombotic events in the angiotensin II group, the open-label study will be stopped. For example, assuming a baseline rate of thrombotic events of 1/10 (10%) in the control arm, if 5/10 patients in the angiotensin II group (50%) experienced a thrombotic event, a Fisher exact test yields $p=0.141$ and the open-label use of angiotensin II would be stopped due to concern for safety. If thrombotic event differences do not meet this threshold, we will continue with the enrollment of an additional 10 patients to meet the 20 patient enrollment set.

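### In the supplied text the only prespecified study-level safety stop is a single look at 10 treated patients, so the plan's own threshold can be met during patients 11 to 20 without triggering anything

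*Combined protocol and SAP*

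**What the plan says.** The rule appears in the Data and Safety Monitoring answer and again under Interim Analysis.

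- Timing: "Following enrollment of the 10 patients in the control arm and 10 patients in the angiotensin II arm", described as "half of the 20 patients that will ultimately receive the drug".
- Test: "Groups will be compared using a Fisher's exact test given the small sample size". Sidedness is not stated.
- Criterion: "if the p-value is 0.15 or less with increased thrombotic events in the angiotensin II group, the open-label study will be stopped".
- Example: "assuming a baseline rate of thrombotic events of 1/10 (10%) in the control arm" and 5/10 on angiotensin II, "a Fisher exact test yields p=0.141 and the open-label use of angiotensin II would be stopped due to concern for safety".
- Otherwise: "If thrombotic event differences do not meet this threshold, we will continue with the enrollment of an additional 10 patients", which brings the treated group to 20.

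Neither section gives a second look, a running count or a trigger after that. Elsewhere, Data Collection lists side effects to be recorded, including venous thromboembolism and new ischemic events. Safety Precautions relies on the monitoring that ICU patients receive anyway. The COVID-19 provision in Research Procedures removes single patients. None of these attaches a study-level threshold to thrombotic events.

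**The concern.** The plan justifies its lenient threshold by concern for safety, and the Background cites a labelled thrombosis warning (13% vs 5%). That concern does not lapse at the tenth treated patient. The plan has already said how much evidence would warrant stopping, but it applies that standard once, when the data are thinnest. Ten of the 20 planned exposures then proceed with no prespecified comparison. The same holds for thrombotic events that surface late in treated patients 1 to 10. What is at stake is whether a signal that meets the sponsor's own criterion at, say, patient 11 would lead to any planned action while nine patients remain to be treated.

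**Working it through.** **1. Reproduce the plan's figure.** For 5/10 vs 1/10 there are 6 events in 20 patients, and C(20,6) = 38,760. The upper tail is [C(10,5)·C(10,1) + C(10,6)]/38,760 = (2,520 + 210)/38,760 = 0.0704. The arms are equal, so the two-sided value doubles it: 0.1409. This matches the stated 0.141; the one-sided value does not. The two-sided test is used from here on.

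**2. The next patient.**
- 4/10 vs 1/10: C(20,5) = 15,504. Upper tail (2,100 + 252)/15,504 = 0.1517, two-sided p = 0.303. Continue.
- 5/11 vs 1/10: C(21,6) = 54,264. Summing all tables no more probable than the observed one gives (4,620 + 462 + 2,772 + 210)/54,264 = 0.149. The criterion is met with nine exposures to come.
- The same happens with other control counts: 3/10 vs 0/10 (p=0.211) then 4/11 (p=0.090); 6/10 vs 2/10 (p=0.170) then 7/11 (p=0.081).

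**3. Stop counts.** Fewest treated events that give two-sided p of 0.15 or less:

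| Control events (of 10) | 0 | 1 | 2 | 3 |
|---|---|---|---|---|
| at 10 treated | 4 | 5 | 7 | 8 |
| at 15 treated | 4 | 7 | 9 | 10 |

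**4. Chance of stopping at the single look.** Let C be control events, T treated events and m_c the stop count. Then P(stop) = Σ_c P(C=c)·P(T ≥ m_c), with C and T binomial on 10 patients. Taking the example's proportions, 10% and 50%, as true rates:

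0.3487×0.8281 + 0.3874×0.6230 + 0.1937×0.1719 + 0.0574×0.0547 + 0.0112×0.0107 = 0.567.

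The look therefore fails to stop with probability 1 − 0.567 = 0.433.

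**5. Add the same comparison at 15 treated.** With k_c the stop count at 15, the added probability is Σ_c P(C=c)·Σ_{t<m_c} P(T=t)·P(Bin(5, p) ≥ k_c − t), where p is the treated event rate. At 10% vs 50% the contributions for c = 0 to 4 are 0.0538, 0.0488, 0.0300, 0.0060 and 0.0006, in total 0.139. So 0.567 + 0.139 = 0.706.

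| True rates, control vs treated | Source | Look at 10 only | Looks at 10 and 15 |
|---|---|---|---|
| 10% vs 50% | plan's example | 56.7% | 70.6% |
| 10% vs 30% | assumed | 18.3% | 32.4% |
| 5% vs 13% | Background | 2.0% | 7.4% |
| 10% vs 10% | assumed | 0.5% | 2.0% |
| 20% vs 20% | assumed | 2.2% | 4.9% |

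The last two rows are false stops.

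**6. What a look at 15 leaves open.** With 1 control event, 5/15 (p=0.345) and 6/15 (p=0.179) both continue, and 7/15 (p=0.088) stops. From 5/11, two or more events are needed in the next four patients. The chance of that is 1 − (1−p)^4 − 4p(1−p)^3: 69% at p = 50%, 35% at 30% and 8% at 13%. Patients 16 to 20 still have no rule.

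**7. Lookup after every treated patient.** Applying the criterion at 10 and after each of patients 11 to 19 (a stop at 20 spares nobody) gives 81.2% at 10% vs 50%. False stopping is 2.7% at 10% and 6.5% at 20% in both arms.

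**The case against.** A single halfway look is a recognisable choice for an open-label study with 20 exposures, and the worked example is close to the edge. 5/11 meets 0.15 by 0.0014, and one further event-free patient (5/12, p=0.162) takes it back above. The exact path of 1/10 control, 4/10 treated and then an event has probability 4.0% at 10% vs 50%, 2.3% at 10% vs 30% and 0.1% at 5% vs 13%. The gain at the cited label rates is also modest: 5.4 percentage points, or about 5 × 0.054 = 0.27 exposures spared per trial. False stopping costs more where background thrombosis is common, and the Background cites an incidence as high as 37.2% in sepsis. All of this stands and limits the size of the point. It does not remove the gap, which the totals in the table show without relying on any one path.

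A reader might infer that safety monitoring ends at patient 10. The documents do not support that. Data Collection records thrombotic and ischemic events with no cut-off, and ICU monitoring continues; what ends is the prespecified comparison. A reader might also infer that the study has no other stop anywhere. That cannot be said either: the attached detailed proposal was not supplied, the extracted text does not show whether a monitoring board was ticked under Research Attributes, and the absence of a written rule does not prevent an ad hoc halt.

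**Conclusion.** The point holds for the supplied text. There is one prespecified study-level comparison, at 10 treated patients, and none for patients 11 to 20. On the plan's own criterion the single look stops 56.7% of the time at 10% vs 50% and 2.0% at 5% vs 13%; a second look at 15 would give 70.6% and 7.4%. This is an inexpensive improvement worth making, and it does not invalidate the design.

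The figures assume a two-sided test, independent events with constant rates, and complete ascertainment at each look. The last is optimistic, because these sections give no follow-up window for thrombotic events, so patients enrolled shortly before a look may be under-counted. Only 5% vs 13% is a treated-versus-control rate taken from the Background. 10% vs 50% is the plan's illustrative observed result read as true rates, and the remaining scenarios are assumptions.

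**What to change.** In both Data and Safety Monitoring and Interim Analysis, state that the same two-sided Fisher comparison, with the same criterion of p at or below 0.15 and more events on angiotensin II, is repeated against the 10 controls after 15 treated patients, counting all events to date in all treated patients. Print the stop counts: 4, 7, 9 and 10 treated events for 0, 1, 2 and 3 control events. Say who carries out the check.

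The cost is one table lookup on data already being collected, with no added patients or staff. The price is more false stopping: 0.5% to 2.0% at 10% in both arms, and 2.2% to 4.9% at 20%. The text should say that this narrows the gap and leaves patients 16 to 20 without a rule.

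If the sponsor wants the gap closed, the same lookup can be applied after each treated patient from 11 on. With 1 control event the counts are 5 of 11, 6 of 12 or 13, 7 of 14 to 16 and 8 of 17 to 19. The price is false stopping of 2.7% at 10% and 6.5% at 20% in both arms.

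If the detailed proposal already contains a later rule, a cross-reference from both sections is enough.
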